9.0 Study Interventions

9.1 Incontinence Information. At the randomization visit, all participants will receive a booklet that includes information commonly given to incontinence patients in clinical practice entitled "Staying Dry: A Practical Guide to Bladder Control - Patient Instruction Booklet". The booklet presents information about urge and stress incontinence, how to locate the pelvic floor muscles, daily pelvic floor muscle exercises, use of pelvic muscles to avoid urine loss and strategies for managing symptoms of urinary urgency.

9.2 Education for the Control Condition. In addition to the incontinence self-help booklet, women randomized to the control condition (entitled the "Structured Education Program"), will be invited to participate in hour long group educational sessions at months 1, 2, 3, and 4. At months 6, 9 and 15, the groups will meet again for informational sessions. The content of these education and support sessions will include information about weight loss, physical activity, healthy eating habits and general health promotion.

9.3 Weight Reduction Program (Months 1-6). Participants in the weight reduction program (entitled the "Lifestyle and Behavior Change Program") will receive an intensive group-based behavioral weight reduction program. They will be taught specific cognitive and behavioral skills to assist in the

modification of their eating and exercise habits. Participants will meet weekly for 6 months in group-sessions led by a nutritionist, exercise physiologist, or behaviorist and will follow a structured protocol. Therapists will not discuss incontinence during the weight reduction program. With this intervention, women are expected to lose an average of 7-9% of their initial body weight in 6 months. The central components of the weight loss program are:

Diet: All participants will be placed on a standard caloric diet (e.g., 1200-1500 kcals/day, depending on initial body weight). The dietary recommendations in this study (< 30% of calories from fat; < 10% of calories from saturated fat) are consistent with the recommendations of the American Heart Association, the American Diabetes Association, and the American College of Sports Medicine.⁶⁵⁻⁶⁷ To help participants initially meet their calorie and fat goals, sample meal plans modeling appropriate food selections will be provided and meal replacement products will be recommended and/or provided to participants. A fat/calorie guidebook will also be given to each participant to be used in the self-monitoring of food intake. Participants will be instructed to monitor food and beverage intake daily.

Exercise: All participants will be encouraged to gradually increase their physical activity until they are exercising 40 minutes per day on 5 days per week. Participants will be encouraged to exercise on their own at home using brisk walking or activities of similar intensity to brisk walking as their primary form of physical activity. Since lack of time is considered the greatest barrier to exercise, participants will be encourage to accumulate the amount of exercise necessary each day by engaging in multiple short bouts of activity (e.g., at least 10 minutes in length). Participants will be instructed to self-monitor their exercise daily. Pedometers will be provided and participants will be encouraged to gradually increase their activity to 10,000 steps per day.

Behavioral skills: To encourage the adoption of the above dietary and physical activity recommendations, the following skills will be introduced in the initial phase of treatment:

- *Self-monitoring*
- *Stimulus control*
- *Problem-solving*
- *Assertiveness training*
- *Social support*
- *Goal setting*
- *Cognitive restructuring*
- *Relapse prevention*

9.4 Weight Maintenance Interventions (Months 7-18). After 6 months of weight reduction intervention, women in the Lifestyle and Behavior Change Program will be cluster randomized at each site by weight reduction counseling group to a skill-based or motivation-based weight maintenance program. Both 12-month maintenance programs will involve group meetings every two weeks. The programs will be matched on contact frequency and duration. The programs will differ in their treatment focus.

9.4.1. Skill-based Approach to Maintenance. The skill-based approach is similar to what is commonly taught in the maintenance phase of standard behavioral weight loss programs. In the skill-based group, months 7-18 of treatment will focus on refining the cognitive and behavioral skills acquired in the first 6 months of treatment. Topics presented in the first 6 months of treatment will be revisited, expanded and refined. The overall goal will be to practice the skills acquired in the first 6 months of treatment so they increasingly become “habits” and to help participants apply these skills in a variety of situations that will occur over the year of maintenance.

9.4.2. Motivation-based Approach to Maintenance. The focus of treatment in the motivation-based group in months 7-18 will be to increase and sustain motivation to utilize the dietary, physical activity, and behavioral skills already acquired. Group sessions will be devoted to the introduction and discussion of exercises designed to 1) increase participants’ satisfaction with their weight loss and incontinence outcomes, 2) decrease participants’ ambivalence about their current behavior change efforts, 3) increase participants’ investment in behavioral choices, and 4) increase participants’ motivation to maintain their new eating and exercise behaviors. Examples of specific group topics and exercises are:

- *Personalized reminders of baseline state*
- *Motivational interviewing*
- *Personal investment in new behaviors*
- *Self-reward*

9.5 Retention of Study Participants

Every effort will be made to retain participants through the 18-month follow-up period. Based on prior experience at the two Clinical Centers, we expect 95% (or 314) of the 330 women to complete the 6-month assessment and 85% (n=280) of participants to complete the 18-month assessment.

The investigative team will encourage retention in PRIDE by educating participants about the importance of the study, encouraging excellent staff-participant rapport, and promoting participant loyalty and identification with PRIDE. Birthday and anniversary notices will be sent and friendly and efficient Clinical Center environments will be maintained. Identifying information including address, phone number, social security number and the name, address and phone number of one family member and two close friends able to locate the subject will also be obtained prior to randomization to facilitate participant-staff contact. Identification with PRIDE will be promoted via the periodic newsletter, refrigerator magnets with the PRIDE logo, and an annual social event for study participants. Participants will be given a stipend of \$25 at both 6 and 12 months and \$50 at 18 months for completing these assessment visits. The coordinating center will monitor the retention rate at all clinics, identifying problems, proposing solutions, and reporting on these matters to the Steering Committee and to the Data and Safety Monitoring Board.

10.0 Serious Adverse Events

The diet and exercise intervention in PRIDE was designed to encourage gradual weight loss in the context of a healthy lifestyle and should pose no added risk to overweight or obese participants. Only serious adverse events as defined by the Food and Drug Administration (death, life-threatening event, inpatient hospitalization or prolongation of hospitalization, persistent or significant disability/incapacity) will be routinely ascertained in this trial. Important medical events may be considered serious adverse experiences at the discretion of the site Principal Investigators if they might jeopardize the participant or

might require medical or surgical intervention to prevent one of the outcomes defined as serious.

Safety-related events will be reported in a timely fashion as required by the Data and Safety Monitoring Board and the IRB.

11.0 Data Management

11.1 Data Collection

The Coordinating Center will develop machine-readable data forms using Cardiff Teleform software. Data forms will be filled out at the clinical sites and sent to the Coordinating Center (CC) via standard fax machines. At the CC, the forms will be received on a server that will use optical character reader (OCR) technology to acquire the data. A CC operator will verify the data manually on screen. This important step corrects many misinterpretations in the automated data input. Verified data are then sent over the local area network (LAN) at the CC to a database on a Microsoft SQL Server. Analog images of the forms are stored in an image-management system on optical disk. The CC does not receive any paper in the process of data acquisition.

11.2 Data Processing

All of the study data are subject to a set of daily error-checking programs. This routine includes checks for completeness, data consistency, and invalid ranges. The results are posted to the study website where clinical site personnel check daily to confirm that the CC has received all of the faxed forms and to address any queries.

A password-protected web site will be the study's data collection hub. Computers at the clinical centers will access a secure and private UCSF CC web server that provides continually updated data summary reports. All reports available on the website will be generated on demand in real time from current study data. The Coordinating Center will provide user accounts and security-enabled web browsers for all clinical center staff.

Clinical centers will respond to queries and edit data forms on the website. As part of the data editing system, the website will also include pages that closely resemble the questionnaires so that clinical staff can view the data that has been accepted into the data system.

Clinical sites will access their data via these pages and address queries. Access to these pages will be restricted to authorized personnel.

12.0 Statistical Analysis, Sample Size And Power Estimates

12.1 General Analysis Considerations

12.1.1. Analysis strategy. The primary analyses will be by intention-to-treat, without regard to adherence to intervention protocols. The major outcome for several of the specific aims are change from baseline in frequency of incontinence episodes, body weight or quality of life. Our primary analysis approach will use mixed linear regression models^{68, 69} to compare the average changes in the intervention and control groups. We will control for Clinical Center as a fixed effect in all analyses. Interactions of the outcomes with Clinical Center will be assessed in exploratory analyses.

12.1.2 Cluster effects. Weight loss groups of 10-20 women will be assembled immediately after randomization and preserved in the second randomization, by group, to motivation-based or skill-based maintenance. There may be correlation of outcomes for members of these groups that would reduce precision and power, increasing sample size requirements. This can be summarized as the design effect, or the ratio of the required sample size to the sample size that would be needed if there were no correlation of outcomes within small groups. Mixed linear models will be used to account for correlations within intervention groups. Fit by restricted maximum likelihood and implemented in SAS Proc Mixed, this method is powerful and accommodates the complex covariance structures that will arise, which will differ by treatment arm. It is also robust to moderate departures from multivariate normality,⁷⁰ but normalizing transformations of the outcome variables will be developed as necessary.

Potential complications due to dropout. In studies of weight loss, participants who drop out early typically regain most or all the lost weight. Under the hypotheses motivating this study, this would imply that most or all improvements in incontinence will also be eroded among study dropouts. The first line of defense in this trial will be to minimize the dropout rates, and to attempt to obtain outcome measurements on participants who are no longer participating in the weight loss intervention. In addition, current practice in

weight loss studies is to impute baseline outcomes for observations missing due to dropout, substantially reducing bias due to "non-ignorable" missingness.^{71, 72} A slight drawback of this procedure is that such singly imputed values are treated as known, so that standard errors on average are too small. To address this potential source of inferential error, we will use multiple imputation of the baseline outcomes with an additive error term derived from the repeated measures model estimate of within-subject residual error. The analysis will then be carried out in the multiple datasets, and the results combined using standard methods to produce summary effect and standard error estimates that properly incorporate the imputation error.^{71, 72} As a sensitivity check, we will also carry out a secondary analysis without imputation, but adjusted for baseline covariates, under the assumption that the data are missing at random ⁷¹ given treatment assignment, the observed outcome values, and baseline predictors of outcome.

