8.2 Randomization Procedures

8.2.1 Randomization to Weight Loss or Control. Women will be randomly allocated in a 2-to-1 ratio to either the weight reduction program or control condition. Randomization will be stratified by clinical center. Blocked randomization within each of the centers will then be performed to ensure that the number of participants in the two treatment groups is close to our goal of an exact 2 to 1 ratio. Since the intervention is not strictly blinded, block size will vary randomly from 3 to 6 in a schedule that is not known to investigators. In addition, to assure an even distribution of treatment groups, a separate set of randomization envelopes will be prepared, as described above, for women who choose to have the urodynamic assessment. Thus, the randomization will be stratified both by center and whether or not the participant volunteers for the urodynamic assessment.

Using computer algorithms for a 2 to 1 randomization, Coordinating Center staff will prepare two sets of sealed, opaque envelopes for each clinical center, color coded for urodynamic assessment or no urodynamic assessment. On the outside, the envelopes will be numbered consecutively with the randomization sequence number; on the inside the envelopes will contain study group assignment. When eligibility has been confirmed by completion of the eligibility checklist, clinical center staff will enter the date, participant's name, and study ID (assigned at the screening visit) consecutively in a randomization log, select the next numbered randomization envelope from the appropriate color-coded series, enter the randomization sequence number listed on the outside of the envelope, then open the envelope and enter the study group assignment contained inside the envelope on the randomization log. All opened and unopened envelopes will be retained at the clinical center for review during study site visits and at the end of the trial. Randomization dates and times should follow the order of the randomization sequence numbers, providing a check on validity. Screening data

will be retained by study ID for women not randomized, facilitating review of the recruitment process.

Participants will be randomized in “waves” of about 30 – 40 at a time to accommodate the formation of intervention or control groups. Eligibility is determined during screening visits.

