12.2 Statistical Methods

12.2.1. Specific Aim #1. *To determine whether randomization to a weight reduction program results in greater reductions in frequency of incontinence episodes at 6 months compared to the control condition.*

Analysis. Our hypothesis is that randomization to the weight reduction group will result in greater reductions in frequency of incontinence compared to the control group. The predictor variable is assignment to the weight loss or control group and the outcome is change from baseline to the end of the weight loss intervention at 6 months in number of incontinent episodes per week, as recorded on the 7-day voiding diary. As described above, we will use mixed linear regression models to compare average changes in the intervention and control groups, controlling for clinical center and taking account of clustering within weight loss groups.

Sample size estimation. In our pilot study of weight loss for treatment of incontinence, the between-group difference in reduction in incontinence frequency was 12 episodes per week (average reductions of 14 vs 2 episodes in the weight loss vs. control groups), with standard deviation (SD) of 14 episodes per week, for a very large standardized effect size of nearly 0.9 SDs. In the proposed study, expected weight loss will be smaller and the control group will receive a self-help booklet that will likely result in some improvement in

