16.2.1 Goals For Structured Education Program

The ultimate goal of all Structured Education Program (SEP) sessions is retention.

Additional goals are as follows:

- Provide valuable learning experience
- Provide enjoyable experience
- Enhance bonding between participants of the SEP group and the Leader
- Provide an opportunity for group support

The Group Leader should identify him/herself as the Group Leader to each respective SEP group. Retention is served when group members are able to identify with one person who they associate as their leader. A bond will develop with the leader as the education sessions continue. The Group Leader should be a PRIDE staff member with a clinical background, such as a behaviorist, dietician, nurse, etc.

Resources for conducting the sessions for the SEP group may be found on the PRIDE website by clicking on the Structured Education Program link, then clicking on Session Documentation. It is critical to thoroughly read all the documents before conducting the SEP sessions.

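### The primary model adjusts only for center and weight-loss-group clustering; adding baseline episodes and the urodynamic stratum, and stating how control groups are handled, would improve it at little cost

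*Protocol*

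**What the plan says.** Section 12.1.1 of the protocol (Amendment #5 text) sets one covariate for the whole trial: "We will control for Clinical Center as a fixed effect in all analyses". Section 12.2.1 defines the primary analysis. It states that the "outcome is change from baseline to the end of the weight loss intervention at 6 months in number of incontinent episodes per week", taken from the 7-day voiding diary, and that the arms are compared by mixed linear regression, "controlling for clinical center and taking account of clustering within weight loss groups". Section 12.1.2 describes clustering in the same terms: "Mixed linear models will be used to account for correlations within intervention groups". It also lets covariance structures differ between arms and allows outcomes to be transformed towards normality. The analyses for Aims 3, 4 and 5 are said to be similar to that for Aim 1.

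Three statements elsewhere bear on this model:

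- Section 8.2.1, on the design: "Thus, the randomization will be stratified both by center and whether or not the participant volunteers for the urodynamic assessment".
- Section 12.1.2, on baseline covariates: they enter only a secondary analysis without imputation, "adjusted for baseline covariates, under the assumption that the data are missing at random".
- Control women are also placed in groups. Section 8.2.1 forms waves so that both intervention and control groups can be assembled, section 8.3.4 gives 1C as an example of a control group, and Operations Manual 4.3 says groups stay together for the trial. Operations Manual 16.2.1 gives each education group an identified leader and lists group support among its goals, along with: "Enhance bonding between participants of the SEP group and the Leader".

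**The concern.** Each omission has a different consequence.

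- **Baseline count.** A comparison of changes is valid in a randomized trial. It is less precise than one that adjusts for the baseline value, unless the diary correlation is close to 1. The baseline diary is a required measure, so the information is there and unused.
- **Urodynamic stratum.** Stratified randomization balances the arms on this factor. Leaving it out of the model means the standard error does not credit that balance.
- **Control groups.** If women in the same education group have correlated outcomes and the model treats them as independent, the standard error is too small and the primary test rejects too often. With 2:1 allocation the control arm contributes two thirds of the variance of the contrast (1/110 against 1/220), so an error there carries weight.

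**Working it through.** **Inputs.** From section 12.2.1: difference 6 episodes/week, SD of change 14, 10% dropout that attenuates the effect in proportion (6 × 0.9 = 5.4), design effect 1.3, N = 330, two-sided 5%. From section 8.2.1: 2:1 allocation, hence 220 and 110. Assumed, because the documents give no value: diary correlation ρ from 0.3 to 0.9, equal SDs at baseline and 6 months, share of outcome variance explained by the stratum, and control design effect. All results use the normal approximation.

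**Step 1: the stated power.** With the design effect on both arms,

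SE = 14 × √[1.3 × (1/220 + 1/110)] = 1.864

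power = Φ(5.4/1.864 − 1.96) = Φ(0.937) = 82.6%.

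This meets the stated 80%; 309 women would suffice for exactly 80%. With 1.3 on the intervention arm only, power is 88.3%. Applying 1.3 to both arms also fits the protocol's other figures better. It gives a detectable effect of 0.414 SD overall and 0.586, 0.655 and 0.757 SD in the 50, 40 and 30% subgroups, against stated values of 0.43 and 0.58, 0.63 and 0.75. The intervention-only version gives 0.381 and 0.539, 0.603 and 0.696.

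**Step 2: baseline adjustment.** With equal SDs σ, the variance of change is 2σ²(1 − ρ) and the residual variance after adjustment is σ²(1 − ρ²). Their ratio is (1 + ρ)/2. Keeping 1.3 on both arms:

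| ρ (assumed) | Variance ratio | Residual SD | Power | N for 80% |
|---|---|---|---|---|
| change score | 1 | 14 | 82.6% | 309 |
| 0.9 | 0.95 | 13.65 | 84.4% | 294 |
| 0.7 | 0.85 | 12.91 | 88.1% | 264 |
| 0.5 | 0.75 | 12.12 | 91.7% | 234 |
| 0.3 | 0.65 | 11.29 | 94.9% | 201 |

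The gain is roughly 2 to 12 percentage points.

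**Step 3: the omitted stratum.** If the stratum explains a share R² of outcome variance, the model's standard error is too large by the factor 1/√(1 − R²). For R² = 0.01 this is 1.005, and for R² = 0.05 it is 1.026. True alpha is then 4.9% and 4.4%, which is conservative.

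**Step 4: control clustering present but not modelled.** Take 1.3 in the weight loss arm and d in the control arm. The ratio of model to true standard error is

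√[(1/110 + 1.3/220) / (d/110 + 1.3/220)].

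| d (assumed) | SE ratio | SE too small by | True alpha |
|---|---|---|---|
| 1.0 | 1.000 | 0 | 5.0% |
| 1.1 | 0.971 | 2.9% | 5.7% |
| 1.2 | 0.944 | 5.6% | 6.4% |
| 1.3 | 0.920 | 8.0% | 7.1% |

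The DSMB meeting schedule plans 14 women per group. At that size, d = 1.1 needs an intraclass correlation of 0.1/13 = 0.008, and d = 1.3 needs 0.3/13 = 0.023.

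**Step 5: number of control groups.** The same schedule randomizes 336 women in sets of 84, which is 4 sets. Each set has 3 groups at each of 2 sites, one of the 3 being control. That gives 4 × 2 = 8 control groups.

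**The case against.** The strongest reply is that this is detail for a statistical analysis plan, which is not at hand. Section 12.1.1 says that center will be controlled for, not that it is the only covariate, and arm-specific covariance leaves a control random effect open. That is fair for the control groups, where the text is silent rather than wrong. It is weaker for baseline. The protocol describes the primary model twice without that term and places baseline covariates in a secondary analysis, whereas Aim 2 does name an adjustment for first-phase weight loss.

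A reader might infer four stronger things, none of which the documents support.

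- That the trial lacks power. It does not: the planned 80% is met without adjustment.
- That 0.5 is the protocol's own correlation for the diary. That figure is a footnote to the quality-of-life table in section 12.2.5.
- That all three omissions corrupt the standard error. Omitting baseline leaves a larger but valid one, omitting the stratum errs on the safe side, and only control clustering could err the other way.
- That the type I error is in fact inflated. No control correlation is given. Before the 6-month endpoint, control women are invited to four one-hour sessions and one at month 6, while the weight loss groups have 24 sessions in 26 weeks (Operations Manual 16.3). Retention is the stated overriding goal of the education sessions. A control design effect as high as 1.3 would therefore be surprising.

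The sample size also appears to apply the design effect to both arms, so it already makes room for control clustering. What is missing is its mention in the analysis.

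**Conclusion.** The point holds as a modest improvement to the primary model, not as a flaw that invalidates the test. Its firmest part is the unused baseline count. Adjusting for it would raise power from 82.6% to between 84% and 95%, given equal SDs at the two times, a diary correlation of 0.9 down to 0.3, a design effect of 1.3 on both arms, and imputation that leaves the SD unchanged. The stratum is a small mismatch between design and analysis: the standard error is about 0.5 to 2.6% too large if the stratum explains an assumed 1 to 5% of variance. Control clustering is the only part that touches validity. Its size (standard error 3 to 8% too small, alpha 5.7 to 7.1%) rests wholly on an assumed control design effect of 1.1 to 1.3, and is nil if control groups do not cluster.

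**What to change.** In sections 12.1.1 and 12.2.1, for the randomized weight-loss versus control comparisons of Aims 1, 4 and 5 and the Aim 3 subgroup models:

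- add the baseline value of the outcome as a covariate;
- add the urodynamic-volunteer stratum as a fixed effect beside center;
- include a random intercept for session group in the control arm as well as the weight loss arm, with variances allowed to differ by arm.

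Leave the stratum out of the urodynamic substudy models, where every woman is a volunteer and the term is constant. Keep Aim 2's existing adjustment for weight lost in the first phase.

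The cost is a sentence or two and no new data. The one real drawback is that the control-group variance would be estimated from only about 8 groups, and so imprecisely.
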